2.3.2 Demographic variables and other baseline characteristics

Demographic and other Baseline data including disease characteristics will be listed and summarized descriptively by treatment group and in total for the FAS.

Categorical data will be presented as frequencies and percentages. For continuous data, N, mean, standard deviation, median, minimum, and maximum will be presented.

2.3.3 Medical history

Relevant medical history and current medical conditions at Baseline will be summarized by system organ class (SOC) and preferred term (PT), and by treatment group for the SAF.

2.3.4 TED and thyroid medical history

Disease history collected at Screening contains information on the TED and thyroid medical history. Descriptive analyses will be done for time since onset of TED symptoms, time since first diagnosis of TED and underlying thyroid condition based on the FAS.

2.4 Treatments (study treatment, rescue medication, concomitant therapies, compliance)

2.4.1 Study treatment / compliance

Descriptive statistics for exposure to study treatment will be provided based on the SAF.

The duration of exposure to study treatment will be summarized by treatment group.

In addition, the number of treatment syringes will be presented by treatment group in frequency tables by visit and cumulatively.

2.4.2 Prior, concomitant and post therapies

Concomitant medications and significant non-drug therapies prior to and after the start of the study treatment will be summarized according to the anatomical therapeutic chemical (ATC) classification system (ATC level 1 and preferred name), by treatment group for the SAF.

Separate presentations will be provided for ophthalmic and non-ophthalmic medications.

Concomitant medications and significant non-drug therapies during the double-blind treatment period and during the follow-up period will be displayed separately.

TED and thyroid treatment history (previous and ongoing treatments for TED) will be included in the tables for prior/ concomitant ophthalmic medications.

2.5 Analysis of the primary objective

Due to premature study discontinuation, purely descriptive analyses will be performed for the primary endpoint. Analysis on primary endpoints will be done based on FAS.

2.5.1 Primary endpoint

The primary endpoint is the proportion of patients achieving overall response.

2.5.2 Statistical hypothesis, model, and method of analysis

The primary endpoint will be presented by treatment group using a frequency table. Superiority testing will be omitted.

2.5.3 Handling of missing values/censoring/discontinuations

The primary endpoint should in principle be available for all patients who do not discontinue the trial prior to the discontinuation by the sponsor. Missing values will not be replaced.

2.5.4 Sensitivity analyses

No sensitivity analyses are planned.

2.5.5 Subgroup analyses

No subgroup analyses are planned.

2.6 Analysis of the secondary objective

2.6.1 Secondary endpoint

The secondary objectives and endpoints are given in [Table 1-1](#).

Analysis of secondary endpoints will be done based on the FAS.

2.6.2 Statistical hypothesis, model, and method of analysis

The secondary objectives will be analyzed in a purely descriptive manner: summary statistics by visit and change to baseline. No testing strategy will be applied.

2.6.3 Handling of missing values/censoring/discontinuations

Missing values of secondary endpoints will not be replaced.

2.6.4 Subgroup analyses

Not applicable.

2.7 Analysis of exploratory objectives

Due to premature study discontinuation, exploratory objectives and endpoints will not be analyzed.

2.8 Safety analyses

Summaries may be performed separately for initial (Baseline to Week 16) period and entire study period (including follow-up). Week 16 is chosen due to the fact that patients may be switched to another treatment at this time. Use of data up to and including the last visit before first switch opportunity provides an unbiased comparison between AIN and placebo; data collected beyond Week 16 are included in analyses which summarize the entire study period.

All listings and tables will be presented by treatment group. Safety summaries include only data from the on-treatment period and follow-up period with the exception of Baseline data that will also be summarized where appropriate (e.g., change from Baseline summaries). The on-treatment period is defined as date of first treatment to (date of last treatment + 84 days).

In addition, a separate summary for death including on-treatment and post-treatment deaths will be provided.

In particular, summary tables for AEs will summarize only on-treatment events, with a start date during the on-treatment period (treatment-emergent AEs) for the DBTP and the entire study period.

Missing data will not be imputed for safety endpoints.

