### Follow-up/open-label retreatment period (Week 16 up to Week 108)

- Proptosis responders (see definition below) at Week 16 will be followed for relapse up to Week 68. If these patients relapse they will be offered a course of open label secukinumab at the time of relapse (see "proptosis relapsers" definition below).
- Proptosis non-responders (see definition below) at Week 16 will be offered the option of open-label secukinumab treatment (with maintenance of blind of initial randomized treatment) for a duration of 16 weeks, i.e., up to Week 32 with last dose at Week 28, as follows:

Open-label secukinumab 300 mg s.c. at Week 16, 17, 18, 19, 20, 24 and 28.

For patients who are proptosis non-responders and who do not receive open-label secukinumab treatment, a follow-up visit (End of Study [EOS]) 8 weeks after the Week 16 Visit should be scheduled. At this EOS Visit, the assessments associated with the Week 24 visit (for responder) should be performed.

• Proptosis relapsers (see definition below) during the follow-up period (from Week 16 onward to Week 68) will be offered the option of retreatment with open-label secukinumab for a duration of 16 weeks (with maintenance of blind to initial randomized treatment) at the time of relapse as follows:

Open-label secukinumab 300 mg s.c., at time of relapse, then at 1, 2, 3, 4, 8 and 12 weeks.

For patients not receiving open-label secukinumab treatment, a follow-up visit (EOS) 8 weeks after the Week 16 Visit should be scheduled, if not yet completed. At this EOS Visit, the assessments associated with the Week 24 visit (for responder) should be performed.

In the event of a major healthcare disruption (e.g., a pandemic or epidemic) that limits or prevents on-site visits, special efforts should be made to conduct the Week 16, R16 and NR16 visits on-site, if feasible. If it is not feasible to conduct these visits on-site, visits to the patient's home, or a virtual visit if a home visit is not feasible, should be attempted.

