### Administration

Administration of all doses of study treatment at the study site should be performed after the study assessments for the specific visit, including blood sampling and QoL questionnaire, have been completed.

The first study treatment administration will occur at the Baseline Visit, after all study scheduled assessments for this visit have been performed (and inclusion/exclusion criteria confirmed) and only after the scheduled blood samples have been drawn.

Prior to administration, the boxes containing the PFS with study treatment solution should be allowed to come to room temperature unopened. Used PFS should be disposed immediately after use in a sharps container **OR** according to local regulations.

The study treatment solution must be injected s.c. in intact areas of the skin. If possible throughout the trial, the study treatment should be administered to one of the following body regions, rotating the injection site from visit to visit: right thigh, left thigh, right stomach, left stomach, upper outer arm (when assisted by site personnel).

All dates and times of injections during the study must be recorded on the appropriate CRF.

In the event of a major healthcare disruption (e.g., a pandemic or epidemic) that limits or prevents on-site visits to the study site, home administration of the study drug is permitted as described above (Section 6.7). Home administration can be performed by the patient, a trained caregiver, or study personnel. Study participants or caregivers will be trained adequately on how to perform administration of the study treatment, if not already trained. If the patient or caregiver is not trained for drug administration and cannot visit the site to undergo training, the site can consider providing suitable virtual training and oversight. A joint decision together with the patient or caregiver should be made as to whether this constitutes sufficient training and oversight.

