#### Novartis Amended Protocol (Version No. 02Track Changes)

#### Page 58 of 99 Protocol No. CAIN457ADE16

Period	Second C	Second Course Treatment Period				Post-Treatment Follow-Up					
Visit name non-responder	Week NR16 	Week NR17	Week NR18	Week NR19	Week NR20	Week NR24	Week NR28	Week NR32	Week NR40	Week NR56	USV 
Days	113	120	127	134	141	169	197	225	281	393	
Visit name relapsers§	Week R0 	Week R1	Week R2	Week R3	Week R4	Week R8	Week R12	Week R16	Week R24	Week R40	USV 
Days since relapse	1	8	15	22	29	57	85	113	169	281	
Proptosis measurement	Х		Х		Х	Х	Х	Х	Х	Х	(X)
Diplopia grading 	Х		Х		Х	Х	х	Х	х	Х	(X)
GO-QoL	Х		Х		х	х	х	Х	Х	х	
Contact Interactive Response Technology (IRT)	х	Х	Х	х	х	х	х	х			
Study drug administration*	Х	Х	Х	Х	Х	Х	Х				

Confidential

\* = Patients who are non-responders at Week 16 or patients who relapse during follow-up receive 16 weeks of treatment with open-label secukinumab.

§ = Relapse can occur at any time during the 52-week follow-up period (i.e., from Week 16 onward to Week 68).

X = assessment to be recorded in the clinical database or received electronically from a vendor. S = source data.

1 = Ophthalmic examination (please refer to Section 8.3.4).

2 = Unscheduled visits (USV) might be required e.g., if patients observe symptoms between scheduled visits or for safety reasons. The safety assessments listed herein may be performed at the discretion of the investigator as needed to resolve the reason for the unscheduled visit. (S)AE assessment and concomitant medications are mandatory for all unscheduled visits.

3 = Kits for urinalysis will be provided by central lab and test is performed locally.

4 = Only applicable for assessments that have not been performed at the W16 Visit in non-responders.

5 = Only applicable for assessments that have not been performed at the Visit at which relapse was diagnosed.

6 = Gorman score/subjective diplopia score (Bahn et al 1987).

() = Parentheses denote assessments that are on a per need basis at investigator's discretion.

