# 10 Safety monitoring and reporting

#### **10.1** Definition of adverse events and reporting requirements

#### 10.1.1 Adverse events

An adverse event (AE) is any untoward medical occurrence (e.g., any unfavorable and unintended sign [including abnormal laboratory findings], symptom or disease) in a clinical investigation patient after providing written informed consent for participation in the study. Therefore, an AE may or may not be temporally or causally associated with the use of a medicinal (investigational) product.

The investigator has the responsibility for managing the safety of individual patient and identifying AEs.

Novartis qualified medical personnel will be readily available to advise on trial related medical questions or problems.

The occurrence of AEs must be sought by non-directive questioning of the patient at each visit during the study. Adverse events also may be detected when they are volunteered by the patient during or between visits or through physical examination findings, laboratory test findings, or other assessments.

Adverse events must be recorded under the signs, symptoms, or diagnosis associated with them, accompanied by the following information (as far as possible) (if the event is serious refer to Section 10.1.2):

- 1. The severity grade:
  - Mild: usually transient in nature and generally not interfering with normal activities.
  - Moderate: sufficiently discomforting to interfere with normal activities.
  - Severe: prevents normal activities.
- 2. Its relationship to the study treatment (suspected: yes or no). If the event is due to lack of efficacy or progression of underlying illness (i.e., progression of the study indication) the assessment of causality will usually be 'not suspected.' The rationale for this guidance is that the symptoms of a lack of efficacy or progression of underlying illness are not caused by the trial drug, they happen in spite of its administration and/or both lack of efficacy and progression of underlying disease can only be evaluated meaningfully by an analysis of cohorts, not on a single patient.
- 3. Its duration (start and end dates) or if the event is ongoing, an outcome of not recovered/not resolved must be reported.
- 4. Whether it constitutes a SAE (see Section 10.1.2 for definition of SAE) and which seriousness criteria have been met.
- 5. Action taken regarding with study treatment.

All AEs must be treated appropriately. Treatment may include one or more of the following:

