2.1.1 General definitions

Study treatment

Novartis will supply the investigational medication listed below:

- 2 × secukinumab 150 mg PFS, s.c.
- 2 × matching placebo 0 mg PFS, s.c.

Eligible patients will be randomized in a 1:1 ratio to one of the double-blinded treatment arms.

Treatment groups

- Randomized treatment:
 - AIN457 300 mg: All patients randomized to secukinumab.
 - Placebo: Patients randomized to placebo.
- Treatment sequence:
 - **AIN457 – AIN457:** Patients randomized to secukinumab and switched to open-label secukinumab treatment in follow-up period (“AIN457 non-responder”).
 - **Placebo – AIN457:** Patients randomized to placebo and switched to open-label secukinumab treatment in follow-up period (“placebo non-responder”).

Frequency of administration

Baseline to Week 16 (Double-blind):

- Secukinumab (300 mg): Baseline, Week 1, Week 2, Week 3, Week 4, Week 8 and Week 12
- Placebo: Baseline, Week 1, Week 2, Week 3, Week 4, Week 8 and Week 12

Week 16 to end of study (EOS) (Open-label):

- Non-responders at Week 16: Secukinumab (300 mg) at Week 16, Week 17, Week 18, Week 19, Week 20, Week 24 and Week 28;
- Responders at Week 16 who relapse thereafter: Secukinumab (300 mg) at time of relapse, then 1, 2, 3, 4, 8 and 12 weeks from time of relapse.

Stratification factor

Patients will be stratified according to current smoking status (up to 20% smokers per arm), since smoking has a well-known impact on treatment efficacy in TED.

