2.1.1.2 Visit and analysis window

Since the actual visit for a subject may not exactly coincide with their targeted visit date, the actual visit date is mapped to a study visit.

The nearest study day window will be utilized to define study visit for laboratory, vital signs, number of doses received, ophthalmological assessments and GO-QoL collected during office visits before dose is administered.

In case of multiple assessments within an analysis window, the day the closest to the scheduled visit day will be used.

Unscheduled visits will only be used when there is no measurement from the scheduled visit in the defined window. In case of multiple assessment values among the same type of visit (i.e., scheduled vs. unscheduled) within the same analysis window, the closest to the scheduled visit

day will be used. In case of equal distances (e.g., same day), the latest assessment value will be used.

For assessments that are not scheduled at all visits (e.g. hematology assessments) the derivation formula is:

- Lower limit = upper limit of previous visit +1.
- Upper limit = integer value of (target day + target day of next visit)/2.

Table 2-1 Study visit windows during DBTP

Study visit	Target day	Study day
DBTP		
Baseline	1	≤1
Week 1	8	2 – 11
Week 2	15	12 – 18
Week 3	22	19 – 25
Week 4	29	26 – 43
Week 8	57	44 – 71
Week 12	85	72 – 99
Week 16	113	100 – 127

Table 2-2 Study visit windows during open-label treatment and follow-up for non-responders

Study visit	Target day	Study day
Week NR 16*	113	100 – 116
Week NR 17	120	117 – 123
Week NR 18	127	124 – 130
Week NR 19	134	131 – 137
Week NR 20	141	138 – 155
Week NR 24	169	156 – 183
Week NR 28	197	184 – 211
Week NR 32	225	212 – 253
Week NR 40	281	254 – 337
Week NR 56	393	338 – 448

*Only applicable for assessments that have not been performed at Week 16 visit in non-responders.

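### The Day 1–Week 16 adverse-event tables have no rule for events starting on the switch day, so an event that follows a placebo patient's first open-label secukinumab injection can be counted under Placebo

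*SAP*

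**What the plan says.** SAP 2.8 plans AE summaries for Baseline to Week 16 and for the entire study. Its reason for the first cut-off is "Week 16 is chosen due to the fact that patients may be switched to another treatment at this time", and it then states: "Use of data up to and including the last visit before first switch opportunity provides an unbiased comparison between AIN and placebo". Data from after Week 16 appear only in the entire-study analyses. AEs are selected by start date.

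In SAP Table 2-3 the double-blind row has two groups, AIN457 and Placebo, and no footnote. Footnotes 1 to 3 belong to the entire-study row. Footnote 2 keeps a placebo patient's pre-switch events under Placebo, and footnote 3 puts post-switch events under Any AIN457.

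On dosing, SAP 2.1.1 has "Non-responders at Week 16: Secukinumab (300 mg) at Week 16, Week 17", and Protocol section 3 has "Open-label secukinumab 300 mg s.c. at Week 16, 17, 18, 19, 20, 24 and 28". Footnote 4 of Protocol Table 8-2 says of the NR16 visit: "Only applicable for assessments that have not been performed at the W16 Visit in non-responders".

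On the order of events within a visit, Protocol 6.7.2 says: "Administration of all doses of study treatment at the study site should be performed after the study assessments for the specific visit". SAP 2.1.1.2 likewise describes "ophthalmological assessments and GO-QoL collected during office visits before dose is administered".

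On timing, Protocol 6.7.2 requires both date and time for injections. For an AE, Protocol 10.1.1 asks for "Its duration (start and end dates" and mentions no clock time.

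**The concern.** The last day of the blinded period and the first day of open-label treatment are the same day. For anything measured at the visit this does no harm, because measurement precedes dosing. An AE is different: it is placed by its start date, and a reaction to the Day 113 injection carries the same date as the end of the blinded period.

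The events most likely to start on an injection day are injection-site and hypersensitivity reactions. The assessment schedules name the former, and Protocol 4.5 lists the latter among the observed risks of secukinumab. In a patient randomized to secukinumab, such an event at least stays with the right drug. In a placebo patient it would be a secukinumab event in the Placebo column, and it could also reach the table of treatment-related AEs. The misattribution therefore runs in one direction, within the only randomized safety comparison the trial has.

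**Working it through.** **1. The plan's own day numbers.** SAP 2.1.1.2 sets a window's upper limit at the integer part of (target day + next target day)/2.
- Week 16: (113 + 141)/2 = 127. The lower limit is 99 + 1 = 100. Table 2-1 gives 100–127, which agrees.
- NR16: (113 + 120)/2 = 116.5, integer part 116. Table 2-2 gives 100–116, which agrees.

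These windows place measurements, not AEs. They confirm that Week 16 and NR16 share target Day 113.

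**2. Is Day 113 inside the blinded period?** Yes. SAP 2.8 includes the Week 16 visit. SAP 2.1.1.5 computes double-blind exposure for completers as Week 16 visit date − first dose date + 1, which on target days is 113 − 1 + 1 = 113 days. The switch day is counted as blinded exposure.

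**3. Is open-label drug given on Day 113?** Yes, for non-responders who accept it. Protocol Table 8-2 marks study drug administration at NR16, Day 113, and its footnote 4 makes NR16 the same occasion as Week 16.

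**4. Which data can cross the line?**
- Laboratory, vital-sign and efficacy values from the Week 16 visit: taken before the dose, so they are blinded-period data.
- AEs: a start date of Day 113 fits both before and after the injection. The event is treatment-emergent either way (SAP 2.1.1.5), and in the double-blind row a placebo patient has only the Placebo column.

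**5. Does any other text settle it?** Table 2-3 footnotes 2 and 3 do not attach to the double-blind row, and they do not say how to treat an event dated on the switch day. Table 5-1 works through onsets on Day 50 and Day 110 with a first treatment of 100 days. Neither onset is on the switch day.

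**6. Size.** SAP section 1 gives 28 randomized, 25 completing the double-blind period and 23 entering follow-up, with no split by arm. SAP 1.2 reports no responders.
- Assumed placebo denominator under 1:1 allocation: 28/2 = 14. One additional patient moves crude incidence by 1/14 = 7.1 percentage points.
- With smaller denominators: 1/12 = 8.3 points and 1/10 = 10.0 points.
- Placebo patients at risk: if follow-up entrants split evenly, 23/2 = 11.5, so 11 or 12 at most under that assumption. Open-label treatment is optional, so the number dosed on Day 113 may be lower.
- Crude incidence counts patients. One already counted for the same preferred term, system organ class or any-AE row adds nothing to that row.

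**The case against.** The strongest reply is that the SAP shows the right intention. It describes the cut-off as preceding the switch opportunity, assessments come before dosing, and footnotes 2 and 3 assign post-switch events away from Placebo. A reader might infer from this point that the SAP directs post-switch reactions to be counted as placebo events. It does not; that outcome follows only from applying an inclusive date rule where no exception is written. This part of the reply stands, and so the point concerns the double-blind tables. For the entire-study tables the principle is already correct and lacks only a same-day convention.

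A second reply is that the answer may lie elsewhere. The AE page of the eCRF might capture onset time, and SAP 2.1 leaves general treatment-arm handling to the TFL shells. Neither is available here. The possibility is real, but the rule affects the content of the main safety tables and belongs in the SAP text.

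A third is that the stakes are low: the study stopped early, all analyses are descriptive, and all AEs will be listed, so Day 113 events can be inspected one by one. SAP 2.8 also says only that separate period summaries may be done. The first part is fair and limits the weight of the point. The last is weaker, because the same section goes on to specify AE summary tables for the double-blind period, and Table 2-4 lists their content.

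**Conclusion.** The point holds as a gap in the rule for the Day 1–Week 16 AE tables. The documents establish that Day 113 lies in the blinded period, that open-label secukinumab may be given that day, that AEs are placed by start date, and that no convention separates events before and after that injection. The comparison described as unbiased is therefore not protected for same-day AEs in placebo patients who switch.

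The size per patient is about 7 points if there are 14 placebo patients and about 10 points if there are 10. It applies only to a patient not already counted in the category concerned. How many such events occurred is unknown. It would be tempting to conclude that the leak narrows or reverses a difference between the arms. The documents do not support that, since they report neither same-day events nor placebo switchers. Nor do they support any suggestion that Week 16 laboratory, vital-sign or efficacy values are contaminated.

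**What to change.** In SAP 2.8 and Table 2-3, extend the logic of footnotes 2 and 3 to the double-blind row and add one same-day convention for both arms. For patients who receive open-label secukinumab, AEs starting on or after the date of the first open-label dose are left out of the Day 1–Week 16 tables and assigned to open-label treatment, unless onset before the injection is recorded or the event was identified at the pre-dose Week 16 assessments. The second exception keeps, for example, an AE raised by a pre-dose Week 16 examination in the same period as that examination. State that Week 16 measurements taken before dosing stay in the blinded period, and use the same convention for the before/after split in the entire-study tables.

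The cost is one or two sentences and a date condition in the programming. Double-blind exposure need not be redefined, because Table 2-4 gives only crude incidence for that period. The downside is that a few same-day AEs with unknown onset time, some of which may have begun before the injection, could leave the blinded period. Flagging Day 113 events in the AE listing would let readers see them.

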#### 12.5.2 Safety endpoints

For all safety analyses, the Safety Set will be used. All listings and tables will be presented by treatment group.

Safety summaries (tables, figures) include only data from the on-treatment period and followup period with the exception of Baseline data that will also be summarized where appropriate (e.g., change from Baseline summaries). In addition, a separate summary for death including on treatment and post treatment deaths will be provided. In particular, summary tables for AEs will summarize only on-treatment events, with a start date during the on-treatment period (treatment-emergent AEs).

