#### Adverse events

All information obtained on AEs will be displayed by treatment group and patient.

The number and percentage of patients with treatment emergent AEs (events started after the first dose of study medication or events present prior to start of double-blind treatment but increased in severity based on PT) will be summarized in the following ways:

- By treatment, primary SOC and PT.
- By treatment, primary SOC, PT and maximum severity.

Separate summaries will be provided for study treatment related AEs, death, SAEs, other significant AEs leading to discontinuation.

The number (and proportion) of patients with adverse events of special interest (AESIs) will be summarized by treatment.

A patient with multiple AEs within a primary SOC is only counted once towards the total of the primary SOC.

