2.1.1.5 Safety endpoints

Discontinuation of treatment due to AE

Discontinuation of treatment due to AE is determined by the information given on the Adverse events eCRF page (action taken=“Drug withdrawn”). “Death” as a reason for treatment discontinuation will be summarized separately.

Treatment-emergent adverse events (TEAEs)

Treatment-emergent adverse events (TEAEs) are defined as adverse events (AEs) that occurred on or after the first dose of study treatment up to 84 days following the last dose of study treatment. In addition, AEs registered prior to start of double-blind treatment are considered as treatment-emergent if they have increased severity based on preferred term any time after the first dose of study treatment.

Serious adverse events (SAEs)

SAEs are determined by the flag on the Adverse Events eCRF page.

Treatment-related adverse event

Treatment-emergent adverse event is defined as treatment-related, if the investigator considered it as having a reasonable possibility to be related to study treatment, which is reflected in the eCRF with a corresponding flag.

Duration of exposure to AIN457 or Placebo (DBTP)

For calculations of exposure duration, last/ first dose date refers to receiving dose (prefilled syringe) > 0.

The duration of exposure to study treatment or placebo is computed as:

For patients completing the DBTP:

- Week 16 visit date – first dose date + 1.

For patients who discontinue treatment during DBTP:

- min (last dose date +84 days, Week 16 visit date) – first dose date + 1.

Duration of exposure to AIN457 (during entire study period)

For calculations of exposure duration, last/ first dose date refers to receiving dose (prefilled syringe) > 0. Duration of exposure will be defined as the time from first dose of study treatment to the time of treatment switch (for subjects who switch treatment) or minimum of (last dose of the treatment + 84 days) and (last visit date). Patients who switch treatment during the study (e.g., from placebo to active treatment) will have exposure to both medications using the appropriate start and stop dates (full details are described in Section 3.1 of the protocol [i.e. study protocol v01 dated 24-Aug-2021]).

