2.8.1 Adverse events (AEs)

In the frame of safety analysis the following treatment-emergent AE types will be considered:

- Any AE
- Study treatment related AE
- AE leading to study treatment discontinuation
- Serious AE (SAE)
- Study treatment related SAE
- SAE leading to study treatment discontinuation
- Death

- RMP risks

All AE tables will be summarized by treatment group.

The Medical Dictionary for Regulatory Activities (MedDRA) version 24.0 or later will be used to code all AEs to a system organ class (SOC) and a preferred term (PT).

An overview table of the number and percentage of patients having each type of AE will be given. Crude incidence and exposure adjusted incidence rates will be provided (see [Section 5.4.3](#) [safety analysis]).

Tables with number and percentage of patients having particular AE summarized by treatment group, SOC and PT will be provided for all AEs listed above except for death. Summaries will be provided for each AE type separately.

For AE type ‘any AE’ tables with number and percentage of patients having particular AE summarized by treatment group, SOC, PT and maximum severity will be provided.

The SOCs will be presented in the alphabetic order and PTs will be ordered within the SOCs by decreasing order of frequency in the secukinumab treatment group.

If a patient reported more than one AE with the same PT, the AE with the greatest severity will be presented. If a patient reported more than one AE within the same primary system organ class, the patient will be counted only once with the greatest severity at the system organ class level, where applicable.

All AEs, deaths, SAEs and AEs leading to permanent treatment discontinuation and leading to study discontinuation and AEs related to COVID-19 will be listed separately. In addition an ocular AE listing with laterality will be provided.

Table 2-4 Overview of analyses on some safety endpoints

Analysis period	AEs & SAEs	AEs by maximum severity	Study treatment related AEs	Notables for vitals, lab criteria
Day 1 – Week 16	•Crude incidence	•Crude incidence	•Crude incidence	•Crude incidence
Entire study phase	•Crude incidence Exposure time adjusted incidence	•Crude incidence	•Crude incidence	•Crude incidence

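### SAP 2.8 limits AE tables to events that start on treatment, while SAP 2.1.1.5 also counts screening AEs that worsen after first dose; depending on how worsening is recorded, such AEs can drop out of the tables

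*SAP*

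**What the plan says.** **The definition.** SAP 2.1.1.5 gives two routes to being treatment-emergent. The first is by onset: the AE "occurred on or after the first dose of study treatment up to 84 days following the last dose of study treatment". The second is by worsening: "AEs registered prior to start of double-blind treatment are considered as treatment-emergent if they have increased severity based on preferred term". The second route has no end date; it runs for any time after first dose.

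**The tables.** SAP 2.8 states that "summary tables for AEs will summarize only on-treatment events, with a start date during the on-treatment period (treatment-emergent AEs". It dates the period as follows: "The on-treatment period is defined as date of first treatment to (date of last treatment + 84 days". The period therefore opens at first dose. SAP 2.8.1 adds that "the following treatment-emergent AE types will be considered", without saying which of the two rules decides membership.

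**The protocol** has the same pair of rules. Section 12.5.2 says that "summary tables for AEs will summarize only on-treatment events, with a start date during the on-treatment period", and its Adverse events subsection counts "events present prior to start of double-blind treatment but increased in severity based on PT" as treatment-emergent.

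**The endpoint.** TEAE frequency is part of the secondary safety endpoint (SAP Table 1-1, item 2.8).

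**The concern.** The worsening route adds something only for a record whose own start date lies before first dose. An event that starts on treatment already qualifies by onset. A start-date filter that opens at first dose removes precisely the records that the worsening route was written to add. Applied literally, 2.8 cancels part of 2.1.1.5, and the tabulated set depends on which section the programmer follows.

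The term governs more than the overall AE row. SAP 2.8.1 applies it to treatment-related AEs, AEs leading to treatment discontinuation, SAEs and risk-management-plan risks. A mild screening event that becomes severe or serious on drug could be absent from all of those rows. SAP 5.8 still carries both terms as alternatives in angle brackets for the public disclosure tables, so the same choice is open there. With efficacy now purely descriptive, the safety tables are a main remaining output.

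**Working it through.** The plan states no figure to reproduce. The check is to apply both rules to each possible pattern.

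| Pattern | SAP 2.1.1.5 | SAP 2.8 tables | Agree? |
|---|---|---|---|
| (a) Starts between first dose and last dose + 84 days | TEAE | in | yes |
| (b) Starts before first dose, no worsening | not a TEAE | out | yes |
| (c) Starts before first dose, worsens within the 84-day limit, same record kept | TEAE | out | **no** |
| (d) As (c), but a new record is opened at worsening | TEAE | new record in | yes |
| (e) Starts before first dose, worsens after last dose + 84 days | TEAE (no end date) | out | **no** |

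Pattern (c) is the main conflict. Pattern (e) is a side effect of the open-ended worsening clause.

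**Can pattern (c) arise?**
- AEs are collected from written consent (protocol 10.1.1), and screening lasts up to 6 weeks, Day -42 to -1 (SAP 2.1.1.1). Pre-dose AE records can therefore exist.
- Conditions already present at consent go to medical history (protocol 10.1.1). This confines the set to AEs arising between consent and first dose.
- Whether the worsening stays in one record is not stated. Protocol 10.1.1 asks that a detected AE be followed until it resolves or is judged permanent, with changes in severity assessed at each visit. That fits one continuing record. SAP 2.8.1 and 5.8 allow several records of the same preferred term in one patient, which fits (d).

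**Event time.** SAP 5.4.3 builds exposure-adjusted rates from the time to first occurrence of a treatment-emergent event. In pattern (c) the only start date precedes first dose, so it gives no valid time, and no other date is named.

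**Size per patient.** 28 patients were randomized (SAP 1), in a 1:1 ratio. Arm sizes are not given. I assume that all 28 were dosed, because the AE denominator is the safety set (SAP 2.2).
- 14 per arm: 1/14 = 7.1 points.
- 12 in an arm: 1/12 = 8.3 points.
- 16 in an arm: 1/16 = 6.3 points.

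These shifts hold for a given row only if the patient has no other qualifying event in that row. The number of such patients is not given, so no total shift can be derived.

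**The case against.** The strongest reply is that nothing need be lost. SAP 2.1.1.5 judges worsening by preferred term, which reads naturally as a comparison across records. SAP 2.8.1 says what to do when a patient has more than one AE with the same preferred term, and SAP 5.8 has a gap rule for consecutive ones. If sites open a new record at worsening, it has an on-treatment start date and passes the filter. The worsening clause is then a harmless clarification. This reply stands as a possibility and makes the loss conditional. It does not settle the matter, because no section states the recording rule and protocol 10.1.1 leans the other way.

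A second reply is that the bracketed label in 2.8 is shorthand for the defined term, so a sensible programmer would use 2.1.1.5. That is probably what the authors meant, and it makes this a drafting conflict rather than a deliberate exclusion. The sentence still states an explicit start-date condition that the definition does not have.

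A reader might infer more: that worsened events vanish from the safety reporting, or that the plan is built to under-report harm. The documents do not support this. SAP 2.8.1 lists all AEs, with separate listings of SAEs and of AEs leading to treatment discontinuation, so the events stay visible there. The affected set is narrow and may be empty. All analyses are to be interpreted descriptively (SAP 3).

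**Conclusion.** The conflict in the text is real, and the protocol shares it. Its effect is conditional. If a worsening is kept in the existing record with a pre-dose start date, SAP 2.8 drops it from the AE summary tables although SAP 2.1.1.5 counts it. If a new record is opened, the two sections give the same tables, apart from worsening after the 84-day limit. Where a loss occurs, it lowers AE counts and leaves the listings intact.

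The size is about 7 points of crude incidence per affected patient (6.3 to 8.3 for arms of 16 down to 12), under the assumptions in the working. The number of affected patients is unknown and may be zero. The point does not call the trial's conclusions into question, but it bears on a stated secondary endpoint and should be settled before the tables are produced.

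**What to change.** Make three changes, all in the SAP:

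1. **Section 2.8:** replace the start-date phrase and its bracketed label by *treatment-emergent AEs as defined in Section 2.1.1.5*, so that one definition governs every AE table.
2. **Section 2.1.1.5:** limit the worsening clause to increases in severity between first dose and last dose + 84 days, matching the onset clause.
3. **Section 5.4.3:** state that the event time for such an AE is the date of worsening if recorded, and otherwise the first visit at which the higher severity was recorded. The fallback is needed because the documents do not show that a date of worsening is collected.

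No protocol amendment is needed. A line in SAP section 4, on changes to protocol-specified analyses, can record the clarification against protocol 12.5.2. The cost is a few sentences. The downside is that reported AE rates may be slightly higher.
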